1.5 Risks and Benefits

C-11 choline is involved in phosphorylation process integrated into phospholipids in the cell membrane as part of phosphatidylcholine, which is vital in prostate cancer cell. The main risk involves the exposure to the radioactivity associated with the C-11 isotope incorporation. This exposure has been calculated to be much lower than the F-18 FDG. In addition, there is no radiation risk related to MR scan. For MR safety concern, each subject will undergo MR safety screening performed by PET/MR technologist prior to imaging.

2 Study Objectives

Primary Objective:

- 1) Test whether a hybrid combination of focused C-11 choline PET/MR and pelvic mpMRI on a PET/MR system is feasible

Secondary Objective(s):

- 1) Determine the efficacy (added values) of a hybrid combination of molecular focused C-11 choline PET/MR and functional and anatomic pelvic mpMRI in comparison with clinical findings.
- 2) Determine the efficacy (added values) of a torso C-11 choline PET/MR in comparison with conventional CT and bone scan in depicting metastasis to lymph node and bone.

3 Study Design

This study will be a prospective study to test and optimize the feasibility of hybrid 3T PET/MR scan in diagnosing and staging high and very high risk prostate cancer patients.

The FDA approved C-11 choline PET tracer at a dose of 12-14 mCi will be administered intravenously prior to fused PET/MR scan, and prior to diagnostic pelvic mpMRI scan while patient lying in the scanner.

In addition, single dose of Gadavist® (Gadobutrol, Bayer) is at no more than 0.1 mmol/kg will be administered intravenously for pelvic mpMRI.

The whole imaging procedure will be conducted on an FDA approved GE SIGNA 3T PET/MR scanner.

The C11-choline PET/MR and pelvic mpMRI findings and results will be compared with serum PSA level, Gleason score, clinical CT and nuclear medicine whole body bone scintigraphy findings, and histopathological results obtained through standard of care management.

Our primary interest is to investigate the feasibility of hybrid C11-Choline PET/MR fusion and pelvic mpMRI in imaging primary prostate cancer.

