3.3 Duration of Participation

Subjects will complete one day of in-department participation. A second study day will consist of a phone call to the subject after completion of day 1.

Human subjects will be subject to Mayo Department of Radiology policies and procedures. Candidates for enrollment will be first queried by the study coordinator for possible exclusion using the departmental MRI safety guidelines for clinical MRI. The study coordinator will review the medical history and use the subject's serum creatinine level to determine his eGFR based on patient age, gender, and ethnicity. If necessary, the subject will undergo a blood test to determine an up-to-date creatinine level, performed at no expense to the subject. eGFR will be determined prior to performing any contrast-enhanced scan.

Patient flow in the nuclear suite

Treated naïve patients with high risk or very high risk prostate cancer (NCCN risk stratification), who require clinical imaging evaluation including 1) pelvic mpMRI, 2) abdominopelvic CT, 3) bone scan, and 4) other imaging studies as clinically indicated.

Informed consent

C-11 choline PET/MR on GE Signa PET/MR System at 3 Tesla at one session (70-80 minutes)

Part 1: C-11 choline torso (multi-station) PET/MR with C-11 choline injection

Part 2: Hybrid (simultaneous acquisition) dedicated focused pelvic PET/MR pelvic multiparametric MRI without and with gadolinium MR contrast.

IMAGING TECHNIQUES**PET/MR scanner/equipment**

Clinical GE SIGNA 3 Tesla PET/MR system

PET/MRI Technique (Figure 1)

1. There are two integrated components of fused PET/MR and focused Pelvic mpMRI
 - a. Indications/Protocols: Primary prostate cancer.

Part	Description of imaging sequences
1	Torso (multi-station) PET/MR fusion scan with injection dose of C-11 choline
2	Hybrid focused (single-station) PET/MR and mpMRI of the pelvis (simultaneous acquisition of pelvic PET/MR and mpMRI without and with IV gadolinium contrast at the same table position)

- Parts 1 and 2 will be done at one session with the patient on the same PET/MR table.
- .
- The entire PET/MR fusion with focused pelvic mpMRI scanning time is 75-80 minutes.

Part 1: Torso PET/MR Fusion Scan with C-11 choline

- Coil: Three pieces of array coils from vertex of head to the level of upper thigh; No use of endorectal coil.
- Patient supine, head first
- Arms down for all procedures
- Metallic objects should be removed from the patient whenever possible

PET Tracer:

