While patient lying on scanner table, 444-518MBq (12-14ⁱ mCi) C-11 choline will be injected as a bolus through a catheter inserted into a large peripheral vein.

Scan Range:

- Routinely from upper thigh to vertex of head, otherwise specified

Scan direction for PET

- Inferior to superior
- Start imaging immediately after the injection of tracer and acquire images with 2–5 minutes per bed position (totally about 5-6 bed positions). The total scanning duration is around 25-30 minutes

MR attenuation correction:

- Simultaneous PET/MR imaging with PET emission data reconstructed in 3D time-of-flight mode at multiple bed positions. During each bed position, coronal Dixon fat/water sequence, in-phase, and out-phase images will be performed for MR segmented attenuation correction.
- Diagnostic quality axial LAVA-FLEX only was obtained simultaneously with PET emission imaging acquisition at each bed position.

Part 2: Hybrid Focused PET/MR and mpMRI of the Pelvis (simultaneous acquisition of pelvic PET/MR and mpMRI without and with IV gadolinium contrast)

MR contrast agent and medicine

- For a contrast-enhanced scan the technologist will load and connect a power injector for administration of contrast material via a peripheral venous access. The contrast material and dose are both determined by the radiologist subject to departmental policy.
- Typically a single dose of Gadavist® (gadobutrol, Bayer) is used for studies of the prostate gland at our institution. The target contrast dose is no more than 0.1 mmol/kg for subjects with eGFR of higher than 30 mL/minute/1.73 m². Those with a GFR of 30 or less will not be admissible to the study. Contrast material is administered at 3 ml/sec followed by a saline flush of 20 ml at 3 ml /sec.
- 1 mg of glucagon will be administered subcutaneously at the start of the scan as an anti-peristaltic. Glucagon will not be given if the patient has a history of DM.

The following multiparametric prostate MR protocol will be applied. Simultaneous PET emission image will also be acquired. The total mpMRI scan time is around 40-50 minutes.

- Multiparametric MRI of the pelvis technique utilizing an institutional clinical MRI protocol.

Sites	Image sequences
Pelvis	
	Axial T1-weighted LAVA-FLEX*
	Axial DWI
Prostate (high resolution with small FOV)	
	Sagittal T2 FRFSE
	Axial T2 FRFSE
	Axial FOCUS DWI
	Coronal T2 FRFSE
	Axial DCE
Pelvis	
	Post Gd ax LAVA-FLEX (water only, fat only)

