5.9.4 Return or Destruction of Study Drug

After injection of the C 11 choline the syringe will be assayed for residual radioactivity, to be used in calculation of the precise injected dose. The syringe will then disposed of in the radioactive container for 3-4 hours, about ten half-life durations of C11-Choline (C11-Choline half-life of 20 minutes).

6 Study Procedures

Patients who have completed or will complete diagnostic body CT scan and nuclear medicine bone scan as part of standard care will be recruited and consented for participation in the study

PET/MRI is preferably scheduled 6 weeks after prostate biopsy to minimize the effects of post biopsy hemorrhage.

6.1 Day 0

Informed consent discussion with subject by research coordinator. Consent form signed by subject. Medical records will be reviewed by study coordinator. Subject's eGFR will be determined. If current serum creatinine level is unavailable, labs will be obtained for review.

Subject will be reminded to drink 48 ounces of water the day prior to study procedures. On the morning of the procedure, subjects will be counseled to fast for four hours prior to the procedure and drink 24 ounces of water.

6.2 Day 1

The patient will be screened for MR safety prior to entering the scan room, which may include the use of ferromagnetic screening.

[figure not shown]
1. Vital signs (sitting blood pressure, heart rate, respiratory rate, temperature) are measured by the radiology nurse, who records the results on the source document.
2. Investigator MD or research coordinator to see patient, review vital signs and discuss study objectives, explain the imaging procedures, answer questions. MD will sign and date the source document.
3. Subject is brought to the PET/MR imaging suite. Total dose of 12-14 mCi C-11 choline is injected I.V.
4. Torso PET/MR fusion scan is completed. Imaging time 20-30 minutes.
5. Pelvic mpMRI with PET data of pelvis completed. Imaging time 40-45.
6. Following completion of imaging, subject will return to the relax room and vital signs (sitting blood pressure, heart rate, respiratory rate and temperature) will be re-checked by

the radiology nurse, with the study coordinator recording the data in the source documents.

7. Subject will be discharged.

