7.2 Statistical Methods

Descriptive Statistics

Descriptive statistics will be used to describe the average time of the total procedure, patients' tolerance and satisfaction level about the procedure. Paired t-test will be used to compare the suspicious lymph nodes and suspicious osseous lesions in the pelvis and extrapelvic regions detected by hybrid C11-choline PET/MR and pelvic multiparametric MRI method and by conventional CT and bone scan to investigate if the new method is able to detect more lymph nodes and osseous lesions compared to the conventional method. Paired t-test will also be used to compare the average SUV of lymph nodes and osseous lesions in the pelvis and extrapelvic regions by new method with that by conventional method to investigate if the new method provided more clarity in terms detecting the lymph nodes and lesions compared to the old method. If the patients' biopsy and surgery results available, sensitivity, specificity, positive predictive value and negative predictive value of detecting malignant lymph nodes and osseous lesions by the new method and by conventional method will be estimated and compared using McNemar's test.

Handling of Missing Data

As the sample size is 20 and imaging is completed over one day, no missing imaging data is anticipated.

Multiplicity

In current project, there is one primary objective and we don't have to adjust for multiple comparison.

Interim Analysis

There will not be interim analysis for the study.

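### The section 7.2 lesion-count comparison is not limited to anatomy that both PET/MR and the conventional tests imaged, so wider coverage can read as better detection

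*Combined protocol and SAP*

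**What the plan says.** **PET/MR coverage.** Section 3.3 gives the torso scan range as "Routinely from upper thigh to vertex of head, otherwise specified", and the coil set-up agrees: "Three pieces of array coils from vertex of head to the level of upper thigh".

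**CT coverage.** The patient flow in section 3.3 describes patients "who require clinical imaging evaluation including 1) pelvic mpMRI, 2) abdominopelvic CT, 3) bone scan", and the list goes on to allow further studies where indicated ("2) abdominopelvic CT, 3) bone scan, and 4) other imaging studies as clinically indicated"). Section 6 describes the CT differently: "Patients who have completed or will complete diagnostic body CT scan and nuclear medicine bone scan as part of standard care". Section 4.2 allows CT and bone scan from other centres if they are of diagnostic quality, and sets no anatomical range. Secondary objective 2 and section 7.1 say only conventional CT.

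**Bone scan coverage.** Section 3 (Study Design) names "clinical CT and nuclear medicine whole body bone scintigraphy findings" among the comparators.

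**Analysis.** Section 7.2 applies a paired t-test to "suspicious lymph nodes and suspicious osseous lesions in the pelvis and extrapelvic regions detected by hybrid C11-choline PET/MR" with pelvic mpMRI, against conventional CT and bone scan, to see whether the new method finds more. Where biopsy and surgery results are available, it then compares accuracy measures with McNemar's test. Section 7.1 sizes the study on a McNemar test of equal accuracy for detecting patients with malignant nodes. Table 1 has separate pelvic rows for nodes and bone. It sets torso PET/MR against CT for torso nodes, and against CT and bone scan for extrapelvic bone.

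The readable text contains no rule that limits a comparison to the region both methods imaged, and none for how an unimaged region is scored.

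**The concern.** A paired count comparison treats the two counts from one patient as measurements of the same thing. Here they may cover different anatomy. A node in a region that CT did not scan adds one to PET/MR and cannot add to CT. A gain in nodes could then come from better detection in tissue both tests saw, or from scanning more of the body. A longer CT range could supply the second, which says nothing about choline PET/MR. For bone the asymmetry runs the other way.

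Secondary objective 2 (added value for nodal and bone metastasis) rests on these comparisons. If the two sources are not separated, a reader of the results cannot tell which one a difference reflects.

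**Working it through.** **1. Coverage side by side**

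| | PET/MR | Conventional | Seen by only one side |
|---|---|---|---|
| Nodes, CT abdominopelvic | upper thigh to vertex | abdomen and pelvis | chest, neck: PET/MR only |
| Nodes, CT includes the chest | upper thigh to vertex | chest to pelvis | neck: PET/MR only, unless scanned |
| Bone | upper thigh to vertex | whole body (bone scan) | below upper thigh: bone scan only |
| Pelvic nodes and bone | covered | covered | none |

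**2. Effect on the section 7.2 counts**

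For patient i, let S be the PET/MR-minus-conventional difference inside the shared region, E ≥ 0 the suspicious nodes PET/MR reports outside that patient's CT range, and L ≥ 0 the bone lesions below the upper thigh on bone scan.

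- Nodes: D = S + E, so mean(D) = mean(S) + mean(E).
- Bone: D = S − L, so mean(D) = mean(S) − mean(L).

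The t-test acts on D. The coverage term has a fixed sign in each case, whether or not the lesions are real, because these are counts of suspicious findings.

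Illustration: assume S = 0 in all 20 patients, and that k patients each have one out-of-field node. With p = k/20, t = √19 × √(p/(1 − p)) on 19 degrees of freedom. The two-sided 0.05 critical value is 2.093.

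- k = 3: t = √19 × √(0.15/0.85) = 1.83, p = 0.083.
- k = 4: t = √19 × √(0.20/0.80) = 2.18, p = 0.042.

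Random variation in S would dilute this. Several out-of-field nodes in one patient would raise both the mean and the variance. The documents give no value for k.

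**3. The section 7.1 test**

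Inputs: n = 20, difference 0.30, discordance 0.31, two-sided 0.05, stated power 82%. The normal approximation Φ[(0.30√20 − 1.96√0.31)/√(0.31 − 0.30²)] gives 70.3%, and exact McNemar gives 56.9%. A one-sided 1.645 gives 81.8%. The stated power is therefore not reproduced as two-sided by these two calculations. That is a separate matter, and this point does not depend on it.

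Expected discordant patients: 0.31 × 20 = 6.2, split (0.31 + 0.30)/2 = 0.305 against 0.005, or 6.1 against 0.1 patients. Exact p-values: 6:0 = 2 × 0.5⁶ = 0.031; 5:0 = 2 × 0.5⁵ = 0.063. One patient is 1/20 = 5 percentage points.

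What a patient whose only positive node lies above the CT range does to this test depends on the reference result:

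- Confirmed malignant: PET/MR right, CT wrong; the pair favours PET/MR.
- False positive in a node-negative patient: PET/MR wrong, CT right; the pair favours CT.
- No pathology: the patient does not enter the pathology-based comparison.

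Only in the first case does coverage help PET/MR. Suppose that case applies to a share f of patients, with equal accuracy in the shared region and 2.5% discordance each way. Enumeration then gives a significant result with probability 0.2% (exact) to 4% (uncorrected chi-square) at f = 5%, 2% to 15% at f = 10%, and 20% to 47% at f = 20%. The values of f are assumptions.

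**The case against.** **Abdominopelvic CT is not fixed as the comparator.** The same list in section 3.3 allows other imaging as indicated, and section 6 says body CT. Some patients may have chest coverage. This stands: the text shows an unsettled CT range, not a known mismatch in every patient. It is also why coverage needs recording.

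**The plan does not say that unimaged disease is a miss.** A reader might infer that it does. The documents are silent, and the readout workflow figure is not reproduced in the available text. What can be said is that nothing readable prevents that scoring. In a plain lesion count it follows without any scoring rule, because an unscanned region contributes zero.

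**The accuracy test may not be biased towards PET/MR.** This stands. A reader might carry the direction over from the counts, but that test needs pathology, and a false-positive chest node would count against PET/MR.

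**Small numbers.** That one patient can separate 5:0 from 6:0 is true of any single reading error at n = 20. It shows how fragile the test is, not how large the coverage effect is.

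**Coverage may be part of the benefit.** Secondary objective 2 speaks of added value, and section 1.1 calls disease beyond the field of view the main limitation of pelvic mpMRI. Comparing whole staging strategies is legitimate. However, section 7.1 tests equal accuracy and section 7.2 asks which method detects more; neither declares a strategy-level comparison. Reporting both serves either reading.

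**Conclusion.** The point holds for the section 7.2 lesion counts. As written, a coverage difference can appear as a detection difference, in favour of PET/MR for nodes wherever CT stops short of the PET/MR range, and in favour of the conventional tests for bone below the upper thigh. Its size cannot be estimated, because the documents give neither the rate of out-of-field disease nor each patient's CT range; the figures above are conditional illustrations. For the McNemar accuracy test the effect depends on what was sampled, and its direction is open.

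A reader might conclude that added value cannot be interpreted at all, or that visceral results are compromised too. The documents do not support either. Pelvic nodes and pelvic bone lie within every test's field and have their own rows in Table 1. The visceral row of Table 1 is not tied to any test in sections 7.1 or 7.2.

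The change is worth making, but in proportion: these are secondary comparisons in a 20-patient pilot whose primary objective is feasibility.

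**What to change.** 1. Reconcile the CT description in section 3.3 (patient flow) with that in section 6, and state what range the comparator CT covers.
2. Add a CRF field for each patient's CT coverage, including CT done elsewhere.
3. In sections 7.1 and 7.2, make the paired nodal comparison on the region covered by both PET/MR and that patient's CT, and the bone comparison on upper thigh to vertex.
4. Report findings outside the shared region separately and descriptively, as the yield of wider coverage. If a whole-coverage comparison is wanted, keep it and label it as a strategy-level result.

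The cost is wording in three or four places and one CRF field. The analysis changes need no additional imaging. The main comparison will contain slightly fewer lesions, and those left out are still reported.

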Objectives	1): Test whether a hybrid combination of focused C-11 choline PET/MR and pelvic mpMRI on a PET/MR system is feasible. 2): Determine the efficacy (added values) of a hybrid combination of molecular focused C-11 choline PET/MR and functional and anatomic pelvic mpMRI in comparison with clinical findings. 3): Determine the efficacy (added values) of a torso C-11 choline PET/MR in comparison with conventional CT and bone scan in depicting metastasis to lymph node and bone.
Number of Subjects	20
Diagnosis and Main Inclusion Criteria	Clinically diagnosed high and very high risk prostate cancer. Adult patients who are able to provide informed consent.
Study Product, Dose, Route, Regimen	C-11 choline PET tracer, One dose, totally 12-14 mCi, intravenous administration while patient is lying on the table
Duration of Administration	1 study day
Reference therapy	None
Statistical Methodology	Descriptive statistics will be used, including sensitivity, specificity, and accuracy, based on histopathological correlation.

1 Introduction

This document is a protocol for a human research study. This study will be carried out in accordance with the applicable United States government regulations and Mayo Clinic research policies and procedures.

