* Axial T1-weighted LAVA-FLEX acquired in Part1. may be used for pre-contrast T1-weighted images.

Image review:

- PET/MR fusion study, including PET emission data, MRAC image and focused pelvis PET/MR fusion images will be sent to MIM Vista workstation for review by an independent, experienced board certified nuclear medicine radiologist without knowing clinical findings except for high risk prostate cancer.
- Focused mpMRI of pelvis images will be sent to PACS for review by an independent, experienced board certified body MR radiologist without knowing clinical findings except for high risk prostate cancer.

Evaluation of imaging findings:

Reviewers review images to evaluation imaging findings without knowing clinical findings except all subjects are recently diagnosed with very high-risk or high-risk prostate cancer. Readout workflow is illustrated in Figure 2. The scores will be recorded and stored in a secured REDCap file.

Pelvic mpMRI:

1. Lesion detection and characterization utilizing PI-RADS version 2 (15).
2. Tumor staging utilizing AJCC TNM staging system (3)
3. Detection of suspicious pelvic lymph nodes.
4. Detection of suspicious osseous lesion in the pelvis.

Torso and focused C-11 choline PET/MR:

1. Lesion detection and characterization.
2. Tumor staging
3. Detection of suspicious pelvic and extrapelvic lymph nodes.
4. Detection of suspicious osseous lesion in the pelvis and extrapelvic regions.
5. Document SUV in the region of interest (ROI) if possible.

Reference standards

[figure not shown]
[figure not shown]

1. Histopathology results when available
2. Clinical imaging study (CT, bone scan, etc).
3. Clinical follow-up (progression or regression at follow-up routine clinical imaging after treatment).

Prostate tumor localization and characterization: Focused C-11 choline PET/MR and pelvic mpMRI findings to be correlated with clinical prostate biopsy and surgery results.

Lymph node metastases: Torso and focused C-11 choline PET/MR and pelvic mpMRI findings to be correlated with clinical CT, lymph node biopsy, and surgery results

Bone metastases: Torso and focused C-11 choline PET/MR and pelvic mpMRI findings to be correlated with whole body bone scan, F-18 NaF PET/CT (if available), CT, dedicated MRI, and biopsy results.

Figure 1. Illustration of Part 1 “Torso C-11 Choline PET/MR” and Part 2 “Hybrid Focused C-11 Choline PET/MR and Pelvic mpMRI.”

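### Section 3.3 lets the comparator scans (CT and bone scan) serve as the reference standard, against the pathology reference used elsewhere, which would bias the accuracy comparison against PET/MR

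*Combined protocol and SAP*

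**What the plan says.** Under the reference-standards heading, section 3.3 lists three items:

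1. "Histopathology results when available"
2. "Clinical imaging study (CT, bone scan, etc", with the bracket closing there
3. "Clinical follow-up (progression or regression at follow-up routine clinical imaging after treatment", likewise

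The lines beneath apply the list by site. For lymph nodes: "Torso and focused C-11 choline PET/MR and pelvic mpMRI findings to be correlated with clinical CT, lymph node biopsy, and surgery results". For bone, the PET/MR and mpMRI "findings to be correlated with whole body bone scan, F-18 NaF PET/CT (if available), CT, dedicated MRI, and biopsy results". The text gives no rule for ranking or combining the three items.

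The same scans are also the comparator. Secondary objective 2 is: "Determine the efficacy (added values) of a torso C-11 choline PET/MR in comparison with conventional CT and bone scan in depicting metastasis" to node and bone. The null hypothesis in section 7.1 and the comparisons in section 7.2 likewise set the new method against conventional CT and bone scan.

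Elsewhere the reference is pathology. The Study Summary says accuracy will be "based on histopathological correlation". Every row of Table 1 has pathology in the reference column, with CT and bone scan in a separate column of clinical exams. Section 3.4 takes biopsy or surgical histopathology as the gold standard. Section 7.2 makes its accuracy measures conditional on biopsy and surgery results being available. Section 7.1 names no reference.

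**The concern.** A test cannot be judged fairly against a rival that also defines the truth. In a patient whose nodal or bone status is set by CT or bone scan alone, the conventional method is correct by construction. Where the two methods agree, both are scored correct. Where they disagree, PET/MR is scored wrong. Disease seen only on PET/MR becomes a false positive, yet finding disease that CT and bone scan miss is the added value that secondary objective 2 looks for.

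Patients without pathology are foreseeable. Section 3 relies on "histopathological results obtained through standard of care management", and the first item in section 3.3 applies only where such results exist. Section 7.1 nevertheless powers an accuracy test on all 20 patients. An analyst who needs a truth value for all 20 could reasonably turn to the second item in section 3.3. The same data would then give one accuracy result under section 3.3 and another under section 7.2.

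**Working it through.** **Inputs from section 7.1.** n = 20, McNemar test, two-sided 0.05, accuracy difference 0.30, discordant proportion 0.31, stated power 82%. The two discordant cells follow:

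- only PET/MR correct: p10 = (0.31 + 0.30)/2 = 0.305
- only CT/bone scan correct: p01 = (0.31 − 0.30)/2 = 0.005

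**Reproducing the 82%.** The large-sample Miettinen formula, with ψ = 0.31 and δ = 0.30, is

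power = Φ{[−1.96ψ + δ√(nψ)] / √[ψ² − δ²(3 + ψ)/4]} = Φ(0.1394/0.1471) = Φ(0.948) = 82.8%.

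This agrees with the stated figure. Full enumeration of the uncorrected McNemar test gives 85.0%, which is the baseline below.

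**Assumptions.** Let f be the share of patients whose truth is CT/bone scan alone, and d the rate at which the two methods disagree among them. The documents give neither. I take f = 10% and 25%, and d from 0.31 (section 7.1's own discordance) down to 0.05. Patients with pathology are assumed to follow section 7.1's inputs.

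**Formulas.** Every disagreement in a scan-only patient counts against PET/MR, so over all 20 patients:

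- p10 = 0.305(1 − f)
- p01 = 0.005(1 − f) + d·f
- expected accuracy difference = 0.30(1 − f) − d·f

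Example, f = 0.10 and d = 0.31: p10 = 0.2745, p01 = 0.0045 + 0.0310 = 0.0355, difference = 0.270 − 0.031 = 0.239.

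If the same patients are instead left out of the test, they contribute no discordant pairs. That is the case d = 0.

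**Results** (probability of a significant result in favour of PET/MR, uncorrected McNemar):

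| f | d | Expected difference | Scan-only patients scored | Same patients left out | Cost of the bias (points) |
|---|---|---|---|---|---|
| 0 | – | 0.300 | 85.0% | – | – |
| 10% | 0.31 | 0.239 | 52.5% | 79.2% | 26.7 |
| 10% | 0.20 | 0.250 | 60.7% | 79.2% | 18.5 |
| 10% | 0.10 | 0.260 | 69.3% | 79.2% | 9.9 |
| 10% | 0.05 | 0.265 | 74.1% | 79.2% | 5.1 |
| 25% | 0.31 | 0.148 | 20.3% | 66.5% | 46.2 |
| 25% | 0.20 | 0.175 | 30.9% | 66.5% | 35.6 |
| 25% | 0.10 | 0.200 | 45.3% | 66.5% | 21.2 |
| 25% | 0.05 | 0.213 | 54.9% | 66.5% | 11.6 |

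The last column isolates the bias. The fall from 85.0% to 79.2% or 66.5% comes only from having fewer verified patients.

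**Sensitivity to the test.** Section 7.1 does not say which form of McNemar's test is meant. With the exact form the baseline is 56.9%. Leaving the scan-only patients out gives 45.6% at f = 10% and 28.4% at f = 25%. Scoring them gives 30.7% to 42.8% and 9.6% to 23.9%. The bias then costs about 3 to 15 points and 5 to 19 points. The direction is unchanged.

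**The case against.** The best defence is that the analysis as specified does not contain the bias. Four places that specify an accuracy calculation or its reference use pathology, and one of them, Table 1, is in section 3.3 itself. The site-specific lines speak of correlation, which can be read as descriptive agreement. Histopathology comes first in the list, which may imply a ranking, and harm needs CT or bone scan to be the sole truth for a patient. Two figures under the heading and the readout workflow in Figure 2 are not shown in the text available here, so a ranking rule may exist there.

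Much of this stands. The bias is conditional: under section 7.2 it is absent. But the second item sits without qualification under a heading that calls it a reference standard, and it contradicts Table 1 whatever ranking a figure may show.

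Two further points are fair. The second item is open-ended and the bone line adds dedicated MRI. A reference that drew on MRI could lean towards the new method, so the direction stated here applies only to truth set by CT or bone scan alone. Also, section 7.1's inputs concern malignant lymph nodes, so nothing is quantified for bone.

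Finally, this is a 20-patient pilot whose primary objective is feasibility. That limits the consequence, but the protocol still states a powered accuracy hypothesis.

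**Conclusion.** The concern holds. Section 3.3 gives CT and bone scan a reference role that conflicts with their role as comparator and with the pathology reference used elsewhere. For any patient whose truth rests on those scans alone, the accuracy comparison can only tie or go against PET/MR.

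Under the assumptions in the table, scoring such patients rather than leaving them out lowers the chance of showing a PET/MR advantage by 5 to 27 points if they are 10% of the sample, and by 12 to 46 points if they are 25%. These figures illustrate the effect and do not predict it, because f and d are assumed and the exact test gives smaller losses. The contradiction in the text does not depend on them.

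The effect is confined to the accuracy comparison. The paired lesion counts in section 7.2 need no reference standard, and the primary feasibility objective is untouched. The point should be fixed before analysis.

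**What to change.** - **Section 3.3:** remove the comparator CT and bone scan from the reference-standard list for the accuracy comparison, so that it matches Table 1, section 3.4 and section 7.2. Label the site-specific comparisons with CT and bone scan as agreement between methods.
- **Reference:** use pathology. For patients without it, report agreement only, or use the follow-up imaging already listed as the third item in a supportive analysis labelled as such.
- **Reporting:** give the number of patients evaluable for accuracy, separately for nodes and for bone, and state possible partial-verification bias as a limitation.
- **Section 7.1:** say that the 82% assumes a pathology result in all 20 patients.

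The cost is mainly wording, but there are real downsides. Fewer patients may be evaluable for accuracy, and the honest power would then be below 82%. Restricting to patients with pathology can bring its own bias, especially for specificity and negative predictive value, because standard care may not provide pathology for everyone. The supportive analysis needs follow-up imaging to be abstracted; section 3.3 already plans to use it, and section 3.7 already names the medical record as a source.
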